7.5 Concomitant Medications, Treatments, And Procedures

All medication prescription and changes, dialysis treatment prescription and changes and other medical care will be the responsibility of the attending dialysis unit nephrologist and other usual physicians. Changes in the above parameters will be recorded by research staff during scheduled study visits.

7.6 Prohibited Medications, Treatments, And Procedures

Participants in the control arm will be asked to refrain from intradialytic cycling during the 26-week "intervention" period. No medications, treatments or procedures will be otherwise prohibited as part of the study.

7.7 Exercise Records

All exercise performed by participants in the control and intervention group will be recorded by participants on a weekly basis in self-reported log sheets.

7.8 Safety Precautions

Staff will wear appropriate PPE as per hospital regulations. Any interaction with patients/participants will follow proper guidelines to limit transmission of COVID-19. Time within the unit will be limited and sanitization of bikes/charts will be completed by hospital-grade sanitizing wipes.

8 Assessment of Safety

8.1 Specification of Safety Parameters

All adverse events (AEs) and serious adverse events (SAEs) will be classified by body system and preferred term according to the Medical Dictionary for Regulatory Activities (MedDRA). AEs and SAEs will be summarized as the frequency of each event in the treatment group.

Frequency tables by treatment group and category of event (e.g., serious, related to study therapy, causing the discontinuation of study intervention) and by National Cancer Institute – Common Terminology Criteria for Adverse Events (NCI-CTCAE) severity grade will be presented. Selected laboratory values will also be summarized in the treatment group using the mean and standard deviation of the change from baseline at scheduled visits.

8.1.1 Definition of Adverse Events (AEs)

An adverse event is any occurrence or worsening of an undesirable or unintended sign, symptom (including an abnormal laboratory finding), or disease that occurs during participation in the trial.

8.1.2 Definition of Serious Adverse Events (SAEs)

An SAE or reaction is any untoward medical occurrence that at any dose leads to any of the following events:

- 1. Death. A death that occurs during the study or that comes to the attention of the investigator during the protocol-defined follow-up must be reported whether it is considered to be treatment related or not.
- 2. A life-threatening event. A life-threatening event is any adverse therapy experience that, in the view of the investigator, places the patient or subject at immediate risk of death from the reaction as it occurred.
- 3. Inpatient hospitalization or prolongation of existing hospitalization.
- 4. Persistent or significant disability.
- 5. An event that requires intervention to prevent permanent impairment or damage. An important medical event that may not result in death, be life threatening, or require hospitalization may be considered an SAE when, based on appropriate medical judgment, it may jeopardize the subject and may require medical or surgical intervention to prevent one of the outcomes listed above.
- 6. Congenital anomaly or birth defect.

8.2 Classification of an Adverse Event

8.2.1 Severity of Event

The study site will grade the severity of adverse events experienced by study subjects according to the NCI-CTCAE Version 4.0 (published May 28, 2009). This document provides a common language to describe levels of severity, to analyze and interpret data, and to articulate the clinical significance of all AEs. Adverse event general grade definitions are summarized as follows:

Grade 1	Mild	Transient or mild discomforts (< 48 hours), no or minimal medical intervention/therapy required, hospitalization not necessary (non-prescription or single-use prescription therapy may be employed to relieve symptoms, e.g., aspirin for simple headache, acetaminophen for post-surgical pain).
Grade 2	Moderate	Mild to moderate limitation in activity some assistance may be needed; no or minimal intervention/therapy required, hospitalization possible.
Grade 3	Severe	Marked limitation in activity, some assistance usually required; medical intervention/therapy required hospitalization possible.
Grade 4	Life- threatening	Extreme limitation in activity, significant assistance required; significant medical/therapy intervention required hospitalization or hospice care probable.
Grade 5	Death	Death.

Adverse events, not included in the NCI-CTCAE, will be recorded and graded 1 to 5 according to the General Grade Definition provided above.

8.2.2 Relationship of an Adverse Event

The relationship, or attribution, of an adverse event in the study will initially be determined by the principal investigator. The PI will also record the determination of attribution on the appropriate CRF and/or SAE report form. The relationship of an adverse event will be defined by using the descriptors provided in the table below.

Code	Descriptor	Definition
UNRELATED	CATEGORY	
1	Unrelated	The adverse event is definitely not related to the study therapy regimen.

RELATED CATEGORIES								
2	Possible	The adverse event might or might not be related to the study therapy regimen (This grade is assigned when uncertainty exists)						
3	Definite	The adverse event is definitely related to the study therapy regimen						

8.2.3 Expectedness

All AEs (grade 2 or higher) that occur after enrollment will be reported.

8.3 Time Period and Frequency for Event Assessment and Follow-Up

Adverse events will be collected from the time the participant completes the first protocol mandated procedure until the subject has completed the study. Adverse events may be discovered through any of these methods:

- Observing the subject.
- Questioning the subject, this should be done in an objective manner.
- Receiving an unsolicited complaint from the subject.
- An abnormal value or result from a clinical or laboratory evaluation.
- Report from HD unit nephrologists or nurses

In association with the attending dialysis unit nephrologist, the PI will provide appropriate medical care to participants experiencing AEs until their symptoms resolve, their status stabilizes, or until 30 days after a participant terminates from the study, whichever comes first.

8.4 Reporting Procedures

8.4.1 Adverse Event Reporting

The PI is responsible for the detection and documentation of events meeting the criteria and definition of an adverse event (AE). All AEs will be recorded in the source documents and on the appropriate CRF(s). All data will be reviewed twice yearly by the DSMB, which may provide recommendations to the study PI about withdrawing any participant and/or terminating the study because of safety concerns.

8.4.2 Serious Adverse Event Reporting

The PI is responsible for the detection and documentation of events meeting the criteria and definition of a serious adverse event (SAE). Serious adverse events will be collected from the time of the randomization until the study completion, or until 30 days after the subject prematurely withdraws from the study.

After learning that a participant has experienced an SAE, the PI is responsible for reporting the SAE as per REB's guidelines. The SAE report will be completed within 7 working days of the reported event. The DSMB may request to receive real-time notification of all SAEs thought to be related to the treatment procedure. At the time of the event, as much information as possible must be collected, but at a minimum must include the following:

- AE description
- Relationship to study exercise intervention.
- Relationship to protocol mandated procedures
- Reason why the event is serious.
- Supplementary CRF pages that are current at the time of SAE reporting: medical history, concomitant medications, demographics, death.

All SAEs will be followed until satisfactory resolution or until the site PI deems the event to be chronic or the adherence to be stable. As additional details become available, the SAE CRF should be updated and submitted to the site's ethics committee.

8.5 Safety Oversight

Safety oversight will be under the direction of an independent DSMB. The DSMB will meet at least annually to assess safety and efficacy data on each Arm of the study. The DSMB will operate under the rules of an approved charter that will be written and reviewed at the organizational meeting of the DSMB. The study PI will provide the DSMB with listings of all SAEs on an ongoing basis. The DSMB may request to receive real-time notification of all SAEs thought to be related to the treatment procedure.

The principal investigator will ensure the timely dissemination of SAE information to the Ethics committee in accordance with applicable guidelines.

9 STATISTICAL CONSIDERATIONS

9.1 Statistical and Analytic Plan

An outline of the analytic methods are given below.

9.2 Sample Size and Power

Based on the limited literature published in this area, we expect an absolute difference of 25% between the intervention and control groups in the proportion of individuals in whom DSI severity score decreases by 7 points or more over time.

We predict DSI score will decrease in 50% of the intervention group and 25% of the control group at 12weeks (baseline prevalence of symptoms assumed to be 50%). A sample size of 58 patients in each arm will allow us to detect this difference with 80% power (alpha 0.05). We conservatively anticipate 30% dropout.⁸³ Therefore, a target sample size of 150 participants (75 participants per study arm) is proposed.

This sample size will allow us to detect a 7-point difference in mean change in DSI severity score using standard deviation of 16 with 80% power and alpha 0.05. This sample size (n=75 in each arm) will also provide 80% power with 0.05 alpha to detect a 12-point difference between groups in mean change in HRQOL measured using EQ-VAS (considered clinically important difference in other chronic diseases)⁸⁵ and a 30% absolute difference in proportion of individuals endorsing deficits in each domain of EQ5D-3L over time assuming 50% baseline deficit and development of new deficits in an additional 10% of the control group and a reduction in deficits in 15% of the intervention group.

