4.2 Study Outcomes

4.2.1 Primary Outcomes

Change in symptom burden from baseline to 12weeks as measured by the Dialysis Symptom Index (DSI) Severity Score (Appendix B-1). This will be measured as the proportion of individuals who have a decline of 7 points or more in symptom burden as defined by DSI symptom severity score from baseline to 12weeks. The DSI is a 30-item self-administered questionnaire with low administrative burden developed to measure the presence (yes/no) and severity ("how much did it bother you" by 5 point Likert-scale ranging from "not at all" to "very much") of common emotional and physical symptoms over the previous week in individuals receiving maintenance HD.⁵¹ Symptom severity scores can range from 0 to 150. A 7-point change in severity score is likely to be clinically significant because this magnitude of change is: a) consistent with the resolution/addition of 1 "very bothersome" symptom plus a 1 point change in severity of 2 symptoms and likely to be significant to patients; and b) is approximately 1 standard error of the mean based on our pilot data (SD 30, n=18) and consistent with distribution-based methods. The DSI has been shown to be reliable in predicting HRQOL in multiple studies in North American and European HD populations.^{6,51}-

Change in symptom burden from baseline to 12weeks as measured by modified DSI Severity Score. Based on our experience and evidence from small clinical trials, we anticipate that the maximum benefit from exercise will occur in a subset of symptoms on the DSI. These include: a) muscle cramps; b) restless legs; c) feeling tired or lack of energy; d) difficulty concentrating; e) worrying; f) feeling nervous; g) trouble falling asleep; h) feeling irritable; i) feeling sad; j) feeling anxious. Thus, we will perform a subgroup analysis of DSI severity scores for the 11 symptoms listed above. This pragmatic approach will lead to less participant burn out than if individual measures were used for each symptom.

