9.3 Description of Statistical Methods

9.3.1 Primary Outcome

Developed in consultation with a statistician ([name], Chronic Disease Innovation

Centre) familiar with RCTs and our study outcomes, analysis will be performed in an intention-to-treat manner on a case available basis. Change in DSI severity score from baseline to 12 weeks will be compared between groups by independent two-tailed t-test or Mann-Whitney U test depending on distribution and using generalized linear mixed models with study timepoint as a random effect and adjusted for baseline DSI score. In a subgroup of individuals whose baseline DSI score is >7, the proportion of individuals whose DSI severity score has improved by 7 or more points from baseline to 12 weeks will be compared between groups at each study time point using Chi-square test.

Multiple logistic regression will be performed to determine predictors of a >7 point change in DSI severity score over time and adjusted for time varying confounders using a marginal structural model. Interaction terms for sex and baseline DSI score will also be inputted into the model. Although study group will be the primary predictor in this model, other key predictors of symptom burden (including baseline DSI score, diabetes status, ischemic heart disease (IHD), age, gender, race, smoking status, serum albumin level, hemoglobin, baseline physical function, physical activity level and interaction terms for gender/intervention and baseline DSI score/intervention) will also be tested in a step-wise manner.

If **missing outcome data** is greater than anticipated (25%) we will impute them according to current FDA/NAS/NRC recommendations using multiple imputation with chained equations ⁸⁶⁻⁸⁸. Specifically, multiple imputation creates 20-40 complete datasets with plausible values from the model-based predictive distributions, and pooled estimates and standard errors are obtained through the use of Rubin's combining rules. These models are predicated on the assumption that the data are missing at random (MAR). Finally, the robustness of the inferences about treatment effects to violations of the MAR assumptions will be evaluated through a sensitivity analysis ⁸⁸.

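### Section 9.2 claims 80% power for two different DSI effects: 50% v 25% responders implies about an 11-point mean difference under normality, and the 80% claimed for a 7-point mean difference is not delivered.

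*Combined protocol and SAP*

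**What the plan says.** - Section 4.2.1 turns the 12-week change in DSI severity into a responder outcome: "This will be measured as the proportion of individuals who have a decline of 7 points or more in symptom burden".
- Section 9.2 sizes the trial on that outcome: "We predict DSI score will decrease in 50% of the intervention group and 25% of the control group at 12weeks". It continues: "A sample size of 58 patients in each arm will allow us to detect this difference with 80% power (alpha 0.05"). It allows for 30% dropout and proposes 75 per arm. A bracketed remark puts the "baseline prevalence of symptoms assumed to be 50" per cent; the synopsis repeats this.
- The next paragraph of 9.2 says the same sample detects a "7-point difference in mean change in DSI severity score using standard deviation of 16", again with 80% power at alpha 0.05. It does not say how this effect relates to the responder effect.
- Section 9.3.1 lists two kinds of analysis under the primary outcome. The continuous change is "compared between groups by independent two-tailed t-test or Mann-Whitney U test depending on distribution" and is also modelled with adjustment for baseline DSI. The responder proportions, in those with baseline DSI above 7, "will be compared between groups at each study time point using Chi-square test". Neither is ranked above the other.

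**The concern.** Once the SD and the shape of the change scores are fixed, a difference in responder rates across a 7-point cut determines a difference in means. Section 9.2 gives both effects with the same sample and the same 80%, so a reader would take a 7-point mean benefit to be covered whichever analysis is used. If the responder contrast needs a larger mean benefit than 7 points, that is wrong. A non-significant responder result could then be read as absence of effect beside a continuous result that shows one. Separately, the 80% for the mean difference can be checked directly and should be right in its own terms.

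**Working it through.** **Inputs.** Responder rates 50% and 25%, 58 per arm, alpha 0.05, power 80%, mean difference 7, SD 16, 75 randomized per arm and 30% dropout are all from 9.2. The 7-point cut is from 4.2.1. Tests are taken as two-sided, as in 9.3.1. Dropout of 30% leaves 75 × 0.70 = 52.5, so 52-53 per arm. The documents give no distribution for DSI change; normal with equal SD in both arms is assumed first, then heavier tails at the same SD.

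**1. The plan's 58 per arm reproduces.** With pooled variance under the null:

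n = [1.96·√(2·0.375·0.625) + 0.8416·√(0.50·0.50 + 0.25·0.75)]² / 0.25² = (1.342 + 0.557)² / 0.0625 = 57.7, so 58. Power at 58 is 80.2%.

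**2. The 80% for 7 points at SD 16 does not.**

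n = 2·(1.96 + 0.8416)²·16²/7² = 82.01, so 83 evaluable per arm.

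Power = Φ(7/(16·√(2/n)) − 1.96):
- n = 75 (no dropout): 76%
- n = 58: 65%
- n = 52-53 (30% dropout): 61%, or 60% with the exact t distribution

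**3. Mean difference implied by 50% v 25%.** With negative change meaning improvement, P(change ≤ −7) = Φ((−7 − μ)/16).
- Control, 25%: μ = −7 + 0.6745·16 = +3.8
- Exercise, 50%: μ = −7.0
- Difference: 10.8 points

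If controls did not change on average, Φ(−7/16) = 33.1% of them would still count as responders.

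**4. Responder-test power for a true 7-point mean benefit.** The shift is 7/16 = 0.4375 SD.
- Control held at 25%: exercise Φ(−0.6745 + 0.4375) = 40.6%; power 43% at 58 per arm.
- Exercise held at 50%: control 33.1%; power 45% at 58 per arm.
- At 52-53 per arm: 40-42%.
- For 80% power: 141 and 133 per arm respectively.

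**5. Sensitivity to shape.** Same SD of 16, t-distributed change with scale 16/√(df/(df−2)), 58 per arm:

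| Shape | Mean difference implied by 50% v 25% | Responder-test power for 7 points |
|---|---|---|
| Normal | 10.8 | 43-45% |
| t, 10 df | 10.0 | 49-52% |
| t, 5 df | 9.0 | 57-60% |
| t, 3 df | 7.1 | about 79% |

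The two effects in 9.2 nearly coincide only at about 3 df.

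**6. The 50% prevalence.** Sections 4.1 and 5.2 (item 6) require DSI above 0, so everyone randomized has at least one symptom. The 50% does not enter the calculation in step 1.

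**The case against.** The strongest reply is that the sentence on 50% v 25% contains no arithmetic error and the rest is modelling. This stands in part.

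- **Shape.** Section 9.3.1 leaves the distribution open. Section 2.1.1 cites a cohort of 698 patients in which 56% did not change, which hints at a peaked shape, although those were patients in their first year on HD, followed for one year, with cut-offs not given. So the 10.8 points and 43-45% must carry the normality condition and the range in step 5. A reader might infer that the plan has controls worsening by 3.8 points; that follows from normality, not from the plan.
- **Benchmark.** In 4.2.1 the 7 points is a change that matters to an individual, and 9.2 attaches the 7-point mean difference to the continuous comparison. Sizing on a 25-point responder difference is a legitimate choice. It still leaves 9.2 with two unlinked effects, and it does not touch step 2, which needs neither responders nor a cut.
- **Pilot SD.** A reader might infer much lower power from the SD quoted in 4.2.1, "based on our pilot data (SD 30, n=18"). The documents do not support a figure: that SD is not said to be of change, it comes from 18 people, and no baseline-to-12-week correlation is given.
- **Replacing the primary.** A reader might infer that the responder outcome should give way to the continuous one. The documents do not support requiring that. Section 9.3.1 already plans the baseline-adjusted continuous analysis. The trial is open-label (7.3.2), registered (10.7) and had participants on study by March 2020 (Appendix 5), so a switch would have to be defended against the charge that it was driven by data.

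**Conclusion.** The concern holds for the power statement in 9.2, not for the choice of outcome. The 80% for a 7-point mean difference at SD 16 is wrong as written whichever sample is meant: about 76% at 75 per arm, 65% at 58, and 60-61% after 30% dropout. This rests on the plan's own figures and the usual t-test calculation.

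The responder and mean effects are different effects unless change is very heavy-tailed. Under normality the responder assumption is worth about 11 points, and the responder test has under 50% power for a 7-point mean benefit; with tails as heavy as t on 5 df it has 57-60%. These figures assume equal SDs of 16, alpha 0.05 and no loss from restricting the Chi-square test to baseline DSI above 7, which can only reduce the numbers. The prevalence assumption contradicts the entry criteria but does not affect the 58.

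**What to change.** In 9.2, and in the synopsis where it repeats the same text:

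1. State the assumed distribution, the SD of change and the control mean change.
2. State that 50% v 25% corresponds to about an 11-point mean difference under normality at SD 16, and give the responder-test power for a 7-point mean benefit with its range: 43-45% under normality at 58 per arm, 40-42% after 30% dropout, and higher with heavier tails, as in the table.
3. Restate the power for the 7-point mean difference as about 76% with no dropout and about 60% after 30% dropout, and note that 80% needs 83 evaluable per arm.
4. Delete the 50% symptom-prevalence assumption.

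Keep the responder primary, and commit to reporting the baseline-adjusted continuous analysis of 9.3.1 beside it. This needs no new patients or data; it is a change of wording, submitted for ethics review as 10.2 requires. The downside is that the stated power becomes less favourable.

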Study Endpoints Primary, Secondary and Mechanistic	Primary outcome: Change in symptom burden over time (12 weeks) as measured by Dialysis Symptom Index (DSI) severity score. Secondary outcomes: Change in generic health-related quality of life over time (12, 26, 52 weeks) as measured by EuroQol 5D-5L and EuroQol visual analogue scale Change in: modified symptom burden (modified DSI severity score); time for recovery post-HD; frailty status (Fried criteria); physical activity level (accelerometer and Godin-Shephard Leisure Time Physical Activity Questionnaire); exercise capacity (Incremental Shuttle Walk Test); self-

	efficacy for exercise (Self-Efficacy for Exercise Questionnaire; hospitalization rate (number hospital days admitted/patient year); all cause 1 year mortality
Brief Summary of Analysis	Sample size : The following assumptions were made: alpha 0.05; power 0.80; 30% dropout and 25% absolute difference in proportion of individuals in whom DSI severity score decreases by 7 points or more (minimal clinically important difference). Therefore, assuming a baseline symptom prevalence of 50% of individuals in each study group, 150 patients (75 in each arm) will be randomized and we will be able to detect a 25% reduction in the primary outcome.
	Primary analysis : Intention-to-treat, available-case basis, in the intervention versus control arm, using Chi-square test and logistic regression for categorical outcomes and t-tests/MannWhitney U for continuous outcomes.
	Secondary outcomes : Descriptive statistics, Kaplan Meier analysis, Poisson regression and linear mixed modeling and will be used as appropriate.

SCHEMATIC OF THE STUDY DESIGN

Enrolment and consent: Once informed consent is obtained, the Dialysis Symptom Index (DSI) will be administered to all participants. Those who score 0 on the DSI (no symptoms) will be deemed ineligible for the study

Randomization: To avoid bias, randomization will be performed following the baseline assessment.

Intervention phase: Participants in "intervention" group will receive study intervention during this time.

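### The 80% power in section 9.2 is overstated: 75 per arm with 30% dropout leaves about 52 evaluable, not 58, and the 7-point claim needs 83 per arm even with no dropout

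*Combined protocol and SAP*

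**What the plan says.** Section 9.2 bases the sample size on the proportion of participants whose DSI severity score falls by at least 7 points: "We predict DSI score will decrease in 50% of the intervention group and 25% of the control group at 12weeks". It continues: "A sample size of 58 patients in each arm will allow us to detect this difference with 80% power (alpha 0.05"). The allowance for loss follows, "We conservatively anticipate 30% dropout", and then the conclusion: "Therefore, a target sample size of 150 participants (75 participants per study arm) is proposed".

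The next paragraph makes a second claim for the same outcome on its continuous scale, namely that the trial can "detect a 7-point difference in mean change in DSI severity score using standard deviation of 16 with 80% power". The alpha there is again 0.05.

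The synopsis (Brief Summary of Analysis) gives the same assumptions together, "alpha 0.05; power 0.80; 30% dropout and 25% absolute difference in proportion of individuals", with 75 randomized per arm.

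Section 9.3.1 says the primary outcome is analysed by intention to treat on available cases. It compares change in DSI with a two-tailed t-test or Mann-Whitney test and with a mixed model adjusted for baseline, and compares responder proportions by chi-square.

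**The concern.** Two statements do not follow from their own inputs. First, 75 per arm is presented as what 58 evaluable becomes after allowing for 30% dropout, but 30% of 75 is more than the 17 per arm that can be lost while keeping 58. Second, the 7-point claim is attached to a sample size too small for it before any dropout.

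Because the analysis is on available cases, power depends on the number with a week-12 DSI, not the number randomized. Section 4.2.1 treats a 7-point change as clinically significant. A null result on mean change would therefore be read as coming from a trial with a 20% chance of missing a 7-point benefit. At the planned dropout that chance is about 40%.

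**Working it through.** **Inputs**
- Responders 50% versus 25%; alpha 0.05; 80% power; 30% dropout; 75 randomized per arm; 7-point difference with SD 16 (all section 9.2).
- Two-sided testing (the t-test in section 9.3.1); 1:1 allocation (section 7.3.2).
- Normal quantiles 1.960 and 0.842.

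**1. Reproduce the 58.** Pooled two-proportion formula without continuity correction, mean proportion 0.375:

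n = [1.960 × √(2 × 0.375 × 0.625) + 0.842 × √(0.5 × 0.5 + 0.25 × 0.75)]² / 0.25² = (1.342 + 0.557)² / 0.0625 = 57.7, so **58 per arm**. This matches the plan.

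**2. Allow for 30% dropout.**
- Required: 58 / (1 − 0.30) = 82.9, so **83 per arm (166 in total)**.
- What 75 leaves: 75 × 0.70 = **52.5 per arm**.
- Dropout at which 75 still leaves 58: 1 − 58/75 = **22.7%**.
- 58 × 1.30 = 75.4, so the plan's 75 looks like multiplication by 1.30 instead of division by 0.70. The plan does not show this step, so the cause is an inference.

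**3. Responder power at the numbers actually analysed** (two-sided 0.05)

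| Evaluable per arm | Corresponds to | Power (normal) |
|---|---|---|
| 58 | 22.7% loss from 75 | 80.2% |
| 56 | about 25% loss | 78.8% |
| 53 | 30% loss, rounded up | 76.5% |
| 52 | 30% loss, rounded down | 75.7% |

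Exact enumeration of the uncorrected chi-square test at 52 per arm gives 77.2%.

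**4. The 7-point claim.** Standardized difference 7/16 = 0.4375. The normal approximation is n = 2 × (1.960 + 0.842)² × 16² / 7² = 82.01, rounded up to 83. The noncentral t calculation gives 82.98, so **83 analysed per arm**. With 30% dropout that means 83/0.70 = 118.6, so 119 randomized per arm (238 in total).

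| Analysed per arm | Power for 7 points, SD 16 (t-test) | Difference detectable with 80% power |
|---|---|---|
| 75 (no loss) | 75.9% | 7.4 points |
| 58 | 64.7% | 8.4 points |
| 52 (30% loss) | 59.9% | 8.9 points |

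The sample size referred to could mean 75, 58 or the expected 52. None gives 80%.

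**5. Could a one-sided test explain it?** One-sided 0.05 would need 65 per arm for 7 points, which 75 satisfies. But the t-test is specified as two-tailed, and a one-sided responder calculation gives 46 per arm, not the plan's 58.

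**The case against.** The strongest reply concerns the size of the problem, not the arithmetic.

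- **The 30% is described as conservative, and another figure appears.** Section 9.3.1 gives 25% as the anticipated missing outcome data. At 25%, about 56 per arm remain and responder power is 78.8%, close to the claim. The plan also does not say whether 30% applies at week 12 or over 52 weeks. This stands as a reason to call the responder shortfall modest. It does not help the 7-point claim, which is about 63% at 56 per arm and fails with no loss at all.
- **Imputation.** Above 25% missing, section 9.3.1 moves to multiple imputation, so at 30% the available-case analysis may not be the whole plan. True, but the power statement does not rely on imputation, and imputation under missing at random does not restore the full information from lost participants.
- **Baseline adjustment.** The mixed model adjusts for baseline DSI. As an illustration, assume the pilot SD of 30 holds at both visits and 16 is the SD of change. The correlation is then 1 − 16²/(2 × 30²) = 0.86 and the adjusted SD is 30 × √(1 − 0.858²) = 15.4. Power at 75 per arm becomes 79%, so the no-dropout gap nearly closes. At 52 per arm it is only about 63%. The plan gives no correlation and does not invoke adjustment in its power claim.
- **Continued recruitment.** Section 5.4.2 allows it if dropout exceeds expectation. The expected figure is 30%, so it does not cover this case.
- **The corrected responder figure is itself conditional.** Section 9.3.1 restricts the chi-square comparison to baseline DSI above 7, and section 9.3.3 sets p < 0.01 for all analyses. If 0.01 governed the primary test, responder power at 52 per arm would be about 52%. This is a fair caution about the replacement wording; both conditions can only lower power further.

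**Conclusion.** The concern holds. The 58 per arm is right, but the 75 per arm said to follow from it is not. At the plan's own 30% dropout the responder comparison has about 76% power (77% exact) instead of 80%, a loss of about 3 to 4 points. The 7-point, SD 16 statement is wrong on any reading: 76% with complete data and about 60% at the planned dropout. It is the more serious of the two.

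These figures assume two-sided alpha 0.05, equal arms, unadjusted tests and, for the responder test, that the baseline DSI restriction removes nobody. The responder shortfall also depends on the 30% applying at week 12; it vanishes at 22.7% or less. The failure of the unadjusted 7-point claim does not depend on dropout.

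**What to change.** Keep 150 participants and correct section 9.2 and the synopsis.

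1. State that 75 per arm with 30% dropout leaves about 52 evaluable per arm and about 76% power for 50% versus 25% at two-sided 0.05, with 80% reached only if dropout is no more than about 23%.
2. Replace the 7-point sentence with the true power of the unadjusted t-test (76% with no loss, 60% at 30% loss), or with the difference detectable with 80% power at 52 per arm (about 8.9 points).
3. Tie these figures to alpha 0.05 and to all evaluable participants, so that they are not read as covering the p < 0.01 rule or the baseline DSI restriction. Say which visit the 30% refers to and reconcile it with the 25% in section 9.3.1.

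The cost is wording only, and a less favourable stated power. Keeping the 80% claims at 30% dropout would instead require 83 randomized per arm (166) for the responder endpoint, or 119 per arm (238) for the 7-point difference.
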